7.2 Food Allergy Episodes

In order to report the occurrence of a safety event associated with accidental food ingestion, subjects will be instructed to contact the site study coordinator or investigator

for any adverse event. The subject may be asked to return to the site. These events will be reported as follows:

- A Food Allergy Episode form will be completed for each of these events in addition to events where consumption of peanut without a reaction occurs.
- If the accidental food ingestion safety event meets the definition of a serious adverse event, as defined below, the AE/SAE form will be completed as well.

7.3 Definitions

7.3.1 Adverse Event (AE) or Medical Event

An **adverse event** is any untoward medical occurrence in humans, whether or not considered drug related which occurs during the conduct of a clinical trial. Any change in clinical status, ECGs, routine labs, x-rays, physical examinations, etc., that is considered clinically significant by the study investigator is considered an AE.

Suspected adverse reaction is any adverse event for which there is a reasonable possibility that the drug caused the adverse event. A reasonable possibility implies that there is evidence that the drug caused the event.

Adverse reaction is any adverse event caused by the drug.

7.3.2 Serious Events (Serious Adverse Events, Serious Suspected Adverse Reactions or Serious Adverse Reactions)

A serious adverse event including a serious suspected adverse reaction or serious adverse reaction as determined by the investigator or the sponsor is any event that results in any of the following outcomes:

- 1. Death
- 2. Life-threatening AE (Life-threatening means that the study subject was, in the opinion of the investigator or sponsor, at immediate risk of death from the reaction as it occurred.)
- 3. Inpatient hospitalization or prolongation of existing hospitalization
- 4. Persistent or significant incapacity or substantial disruption of the ability to conduct normal life functions
- 5. Congenital abnormality or birth defect
- 6. Important medical event that may not result in one of the above outcomes, but may jeopardize the health of the study subject or require medical or surgical intervention to prevent one of the outcomes listed in the above definition of serious event.

7.3.3 Unexpected Adverse Event

An adverse event is "unexpected" when its nature (specificity) or severity is not consistent with applicable product information, such as safety information provided in the package insert, the investigational plan, the investigator's brochure or the protocol.

7.4 Data Monitoring Committee

Although the safety of peanut OIT overall is well established, a Data Monitoring Committee (DMC) has been established to monitor the study for safety. The DMC Charter is under development and a plan has been drafted.

7.5 Toxicity Grading

The study site assigns toxicity grades to indicate the severity of adverse experiences and toxicities. The CoFAR adopted usage of NCI-CTCAE v 4.0 for application in adverse event reporting and will likewise be used for this protocol. The allergic reactions in this protocol are defined beyond the NCI-CTCAE system, and include further characterization of anaphylaxis. Anaphylaxis is characterized as mild, moderate, or severe in **Appendix 3**, independent of the toxicity grade associated with the event. Toxicity grading for allergic reactions including anaphylaxis is modified from the NCI-CTCAE system to be more appropriate for this study population, and is displayed in **Table A4-2** in **Appendix 4**.

The NCI-CTCAE v 4.0 was specifically reviewed for this protocol and is appropriate for this study population. The purpose of using the NCI-CTCAE system is to provide standard language to describe toxicities and to facilitate tabulation and analysis of the data and assessment of the clinical significance of treatment-related toxicities.

The NCI-CTCAE provides a term and a grade that closely describes the adverse event. Each participating site will receive copies of the grading scales and event descriptions.

Record adverse events not included in the NCI-CTCAE listing and grade them 1 to 5 according to the General Grade Definition provided below:

Grade 1	Mild	Transient or mild discomforts (< 48 h), no or minimal medical intervention/therapy required, hospitalization not necessary (non-prescription or single-use prescription therapy may be employed to relieve symptoms, e.g., aspirin for simple headache, acetaminophen for post-surgical pain).
Grade 2	Moderate	Mild to moderate limitation in activity, some assistance may be needed; no or minimal intervention/therapy required, hospitalization possible.
Grade 3	Severe	Marked limitation in activity, some assistance usually required; medical intervention/therapy required, hospitalization possible.
Grade 4	Life-threatening	Extreme limitation in activity, significant assistance required; significant medical/therapy intervention required, hospitalization, or hospice care probable.
Grade 5	Death	Death

For additional information and a printable version of the NCI-CTCAE v. 4.03 manual, consult the NCI-CTCAE website, http://ctep.cancer.gov/reporting/ctc.html.

7.5.1 Guidelines for Determining Causality of an Adverse Event

The investigator will use the following question when assessing causality of an adverse event to study product: Is there a reasonable possibility that the study product caused the event?

An affirmative answer designates the event as a suspected adverse reaction.

7.6 Adverse Events Collection Procedures

Any new event or experience that was not present at Screening, or worsening of an event present at Screening, is considered to be an AE. Unchanged, chronic conditions are not AE's and should not be recorded on the AE page of the CRF. Adverse events will be evaluated from the onset of the event until the time the event is resolved or medically stable, or until 30 days after the subject completes study treatment, whichever comes first.

AEs may be discovered through any of these methods:

- Observing the subject
- Questioning the subject, which should be done in an objective manner
- Receiving an unsolicited complaint from the subject
- Review of medical records/source documents
- Review of home dosing symptom logs (provided to record symptoms between visits

7.6.1 Recording and Reporting Procedures

A multi-page adverse event form will be used allowing all adverse events to be submitted through a single reporting mechanism. Serious adverse events will require additional information reported on additional pages within the Internet data entry system. Source documents, with subject identifiers redacted, can be scanned and attached to the adverse event form as well. The investigator will treat subjects experiencing adverse events appropriately and observe them at suitable intervals until their symptoms resolve or their status stabilizes.

7.6.2 SAE Recording and Reporting Procedures

Serious adverse events will be recorded on the adverse event case report form (CRF). All centers are obligated to report SAEs within 24 h of their occurrence and/or the site's knowledge of the event to the Coordinating Center. The following attributes will be assigned:

- Description
- Date of onset and resolution (if known when reported)
- Severity
- Assessment of relatedness to test article

• Action taken

The site investigator will apply his/her clinical judgment to determine whether an adverse event is of sufficient severity to require that the subject be removed from treatment. If necessary, an investigator will suspend any trial procedures and institute the necessary medical therapy to protect a subject from any immediate danger.

Subsequent review by FDA, the DMC, Institutional Review Board (IRB), or the sponsor(s) may suspend further trial treatment or procedures at a site. The study sponsor(s) and the FDA retain the authority to suspend additional enrollment and treatments for the entire study as applicable.

A subject may voluntarily withdraw from treatment due to what he/she perceives as an intolerable AE, or for any other reason. If voluntary withdrawal is requested, the subject should be asked to continue (at least limited) scheduled evaluations, complete a study termination form, and be given appropriate care under medical supervision until the symptoms of any AE resolve or their condition becomes stable.

7.6.2.1 Reporting Criteria

- 1. Notify the site's investigator.
- 2. Complete and transmit an AE Form through the Internet data entry system. Information regarding a SAE report must be recorded in the subject's medical chart.
- 3. SAE follow-up reports should include hospital admittance notes, hospital discharge summary, clinical notes, resolution date, treatment and any other pertinent information regarding the event. Reporting should not be delayed in order to provide these documents.
- 4. In the event of a death, the SAE Form must be completed and transmitted along with other supporting data (e.g., death certificate, medical notes, etc.).

7.7 Serious Adverse Event Notification

7.7.1 Notifying the Sponsor

Study investigators will provide the Coordinating Center with data of all SAEs as defined per the protocol on an ongoing basis.

The CRO Medical Monitor is responsible for notifying the sponsor and will do so simultaneously with the reporting to the clinical database. As noted above, this should be within 24 h of site awareness of the event. The sponsor's Medical Monitor will review each SAE report and will determine whether the SAE must be reported to FDA on an expedited basis. The final decision for disposition regarding reporting to the FDA rests with the sponsor's Medical Monitor. The IND Sponsor is responsible for submitting the SAE reports to FDA. The IND Sponsor will provide the DMC and the Coordinating Center with copies of any SAE reports submitted to FDA by the sponsor.

The Coordinating Center will provide these expedited reports to the individual site investigators. Events that are serious, related to therapy and unexpected will be reported to FDA in 15 days or for deaths and life threatening events in 7 days (per 21 CFR 312.32).

7.7.2 Notifying the Data Monitoring Committee

The Coordinating Center will provide the DMC with listings of all SAEs on an ongoing basis. Furthermore, the DMC will be informed of expedited reports of SAEs. Reports from DMC ongoing protocol safety reviews will be sent to the investigators.

Per DMC request, centers are instructed to report episodes of anaphylaxis within 24 h of their occurrence and/or the sites being notified of the event to the Coordinating Center if the event is associated with any of the following:

- An emergency room visit;
- Hospitalization;
- More than 2 doses of epinephrine being given as treatment for the same episode;
- Assessment of the anaphylaxis as severe, as defined in **Appendix 3**.

An initial Anaphylaxis Episode form containing the information known to the site at this time will be transmitted to the Coordinating Center. The Coordinating Center will then relay to the sponsor and DMC the individual anaphylaxis reports as they are obtained. The investigational site will supplement the initial Anaphylaxis Episode report with additional information pertaining to an event as it becomes available and will forward the information to the Coordinating Center.

7.7.3 Notifying the Institutional Review Board and Ethics Committee

The investigator will ensure the timely dissemination of all AE information, including expedited reports and DMC safety reviews, to the IRB in accordance with applicable local regulations and guidelines.

7.8 Other Safety Assessments

7.8.1 Physical Examination and Vital Signs

Physical examinations will be conducted at visits indicated in **Appendix 1** Schedule of Events. Height and weight will also be recorded. Vital signs will also be assessed, including blood pressure (BP), pulse rate (PR), and body temperature.

7.8.2 Prior and Concomitant Medications

Prior and concomitant medications will be duly documented in the CRF.

7.8.3 Pregnancy Test

All female subjects of child-bearing age will undergo a serum pregnancy test at screening and then urine pregnancy test at subsequent visits.

7.9 Stopping Rules

7.9.1 Overall Stopping Rules

The study will be suspended at any time such that a treatment-associated death occurs, or that the second of two subjects is admitted to the hospital as a direct consequence of dosing with study medication. The DMC will also be continually reviewing unblinded safety data, and can also recommend, in its judgment, halting the study for any substantial imbalance in adverse events, apart from dosing symptoms. The study will not be resumed until this information has been discussed with FDA and the FDA concurs with resumption of the study.

Allergen Research Corporation additionally reserves the right to discontinue the study at any time for any reason.

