1.2 Peanut OIT

Varshney et al¹⁵ conducted a double-blind placebo controlled study of an OIT protocol in subjects with severe allergy to peanut protein and consistently demonstrated an increase in the dose of allergen tolerated by the subjects versus baseline with a good safety profile.

In addition, peanut OIT has been administered under IND (Investigational New Drug Application) at Duke and Arkansas and under a separate IND at Stanford.^{*} A total of 44 cases from Duke/Arkansas were analyzed and 14 cases from Stanford. Efficacy was demonstrated in 26 cases (17 active and 9 placebo) matching the published information. Sixteen out of 17 active subjects were escalated to a dose between 2400 and 4000 mg over a year. Oral food challenge results were significantly better for the active treatment group than the placebo group where both groups tolerated a mean of 12 mg of peanut protein at baseline, while at one year the mean for the active treatment group was 5000mg of protein and for the placebo group 280 mg of peanut protein (P < 0.001 by Wilcoxon rank-sum test).¹⁵

Dosing symptoms were typical for OIT protocols including rash, wheezing, rhinorrhea, sneezing, itching, abdominal pain, nausea, vomiting, and diarrhea. Symptoms were noted in both the active treatment and the placebo group. Of the 39 cases on active treatment, 4 doses of epinephrine were administered – 2 during dosing and 2 during double-blind, placebo controlled food challenges (DBPCFCs). The Stanford data reported on 14 subjects who were dosed with peanut OIT and dosing symptoms severity and rate were similar to those reported in the Duke/Arkansas data.

These published findings, along with the additional clinical data, are the basis for a Phase II trial to investigate peanut OIT for efficacy and safety in desensitizing peanut allergic subjects. Protocol ARC001 is designed to be a double-blinded, placebocontrolled study establishing the efficacy of CPNA for conducting oral immunotherapy. Protocol ARC002 and any additional follow-on studies will be related but separate openlabel protocols designed to demonstrate the safety of daily dosing with CPNA for an extended period (months to years), to confirm unblinded the efficacy of OIT with CPNA at a dose of 300 mg/d of peanut protein in the former ARC001 placebo population, to provide an option to explore unblinded the safety and tolerability of OIT, and to maintain any desensitization that may have been achieved by subjects.

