dose reduction) or a 2-step dose reduction as their next day's dose (Day 3) in the Clinical Research Center. If this dose is tolerated, it will be continued as the daily home dose for the normal time interval, then escalation attempted in the Clinical Research Center as noted below. If this dose is not tolerated, then the next dose will be a further 1-2-step reduction in dosing (per investigator judgment), and the dose will be given in the Clinical Research Center (Day 4). If this next dose is not tolerated, then a discussion with the Medical Monitor will ensue to make a decision about whether to continue the subject on study-product treatment in the study.

If more *severe symptoms* occur, defined as:

- Skin severe generalized urticarial/angioedema/erythema
- Respiratory laryngeal edema, throat tightness with hoarseness, wheezing with dyspnea, stridor
- GI significant severe abdominal pain/cramping/repetitive vomiting and/or diarrhea
- Neurological change in mental status
- Circulatory clinically significant hypotension (see Appendix 3).

The action should be to treat the subject, and at the physician's discretion either 1) have them return to the Clinical Research Center the next day (Day 2) for dosing with a 2-step reduction in dose under observation or 2) discontinue them from the study product treatment. If the subject tolerates the dose reduction, then they will remain on that dose for 2 weeks and then return to the Clinical Research Center for the dose escalation. A discussion with the Medical Monitor may ensue to make a decision about whether to continue the subject on study product treatment in the study.

If a subject fails dose escalation after three consecutive attempts (with 2-4 weeks between), he/she will be considered an escalation failure and the last tolerated dose will be accepted as the maintenance dose (to Week 24). If the dose escalation is completed with no symptoms, subjects should be observed for 30 min. If the subject exhibits mild symptoms, the duration of the observation period should be 1-2 h post-protocol. For moderate to severe symptoms, the observation period should be at least 4 h and up to 24 h based on symptoms and the treatment regimen needed to stabilize the subject's condition.

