7.1 Definitions for Recording of Safety Events

All safety events observed under this protocol are reported through the data system for the duration of the study. Some safety events arising under certain defined conditions are recorded on specific forms as follows.

- Safety events related to accidental food exposure are recorded on a Food Allergy Episode form and are not reported on an adverse event form unless the event is considered a serious adverse event, as defined below (Section 7.2).
- Any allergic symptoms due to dosing will be recorded directly on the Escalation Dosing form (also referred to as a Study Product Administration form).
- For any event occurring after a subject has signed the informed consent form that meets the definition of anaphylaxis, an Anaphylaxis Episode form will be completed and forwarded to the Coordinating Center within 24 h of its occurrence and/or the sites being notified of the event (see also Section 7.7.2), if the event is associated with any of the following:
 - An emergency room visit;
 - Hospitalization;
 - More than 2 doses of epinephrine being given as treatment for the same episode;
 - Assessment of the anaphylaxis as severe, as defined in Appendix 3.
- If any safety event meets the definition of a serious adverse event (whether or not related to dosing), it will also be recorded on an adverse event (AE)/serious adverse event (SAE) form. Skin prick test and food challenge reactions that occur in the clinic are captured on study specific forms and are not reported on an adverse event form unless the event is considered a serious adverse event, as defined below. All serious adverse events are reported on the AE/SAE form set in addition to the Skin Prick form or an Oral Food Challenge form if the event occurred during one of these procedures. All other safety events that occur throughout the study are reported on the AE/SAE form set.

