## **10.6** Symptoms During Escalation Dosing

During each escalation dosing, the severity of pre-specified symptoms is similarly rated as none, mild, moderate, severe, or life-threatening. In addition, the presence of dose-limiting symptoms and whether the dose was tolerated is recorded for each escalation dose.

Symptoms will be listed by subject, time point, and dose level. Maximum severity by symptom, maximum overall severity, and presence of any dose limiting symptoms will be summarized across all dose levels. Symptoms, maximum severity of any symptom, presence of dose limiting symptoms, and whether the dose was tolerated will be summarized for each dose level. If a subject is administered the same dose at more than 1 up-dosing visit (either the subject remained at the same dose as the previous visit, or a subject had a prior dose increase and subsequent dose reduction), the most severe symptoms and dose-limiting symptoms will be summarized for that dose level.

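### Protocol 7.9.1 excludes dosing symptoms of any severity from the DMC halting criterion, so severe reactions that are non-fatal, judged non-serious and not admitted meet no written study-level criterion

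*Protocol*

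**What the plan says.** Protocol 7.9.1 has two mandatory triggers for suspending the study: a treatment-associated death, and the second subject admitted to hospital as a direct result of dosing. It then says that the DMC reviews unblinded safety data continually and may, in its judgment, recommend "halting the study for any substantial imbalance in adverse events, apart from dosing symptoms".

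Neither document defines dosing symptoms. Protocol 1.2 gives the usual picture from earlier work: "Dosing symptoms were typical for OIT protocols including rash, wheezing, rhinorrhea, sneezing, itching, abdominal pain, nausea, vomiting, and diarrhea". Elsewhere the term is used without an upper limit. Protocol 7.1 says "Any allergic symptoms due to dosing will be recorded directly on the Escalation Dosing form", and SAP 10.6 says that at each escalation dose "the severity of pre-specified symptoms is similarly rated as none, mild, moderate, severe, or life-threatening".

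Severe reactions without admission are foreseen. For a severe reaction in build-up, 6.8.2 tells the site to treat, and then either to stop study product or to "have them return to the Clinical Research Center the next day (Day 2) for dosing with a 2-step reduction in dose under observation". The general Grade 3 definition in 7.5 reads "Marked limitation in activity, some assistance usually required; medical intervention/therapy required, hospitalization possible", and Table A4-3 for allergic reactions likewise makes admission possible rather than expected.

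Serious events are handled separately. Protocol 7.1 says "If any safety event meets the definition of a serious adverse event (whether or not related to dosing), it will also be recorded" on the AE/SAE form, and 3.7 lists dosing symptoms, AEs and SAEs as three items.

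**The concern.** Severe allergic reaction to dosing is a main hazard of peanut OIT, and much of this population is paediatric. Excluding expected mild and moderate symptoms from an imbalance criterion makes sense, because an excess on CPNA is certain and would say nothing new. That reason does not extend to severe reactions, which Protocol 1.6.1 expects in fewer than 1% of subjects. As worded, the exclusion treats both alike. Someone applying 7.9.1 literally would leave an excess of severe, non-serious dosing reactions out of the one DMC halting criterion that the protocol states.

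**Working it through.** **Step 1. Trace one case through the rules.** Take stridor at an up-dosing visit, treated in clinic with one dose of epinephrine, resolved, not admitted, and judged non-serious by the investigator.

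| Rule | Is it met? |
|---|---|
| 6.8.2 severity | Severe; stridor is on the list |
| 7.9.1, death | No |
| 7.9.1, second admission | No |
| 7.9.1, DMC imbalance criterion | Excluded, as a dosing symptom |
| 7.7.2, SAE listings and expedited reports | No, because judged non-serious |
| 7.7.2, 24-hour anaphylaxis report | Not necessarily: it needs anaphylaxis with an emergency room visit, admission, more than 2 epinephrine doses, or severe staging in Appendix 3, which puts stridor under moderate and keeps severe for hypoxia, hypotension or neurological compromise |
| 6.8.2, mandatory discontinuation | No, unless hypoxia, hypotension, mental-status change or aggressive therapy is present |

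The event would reach the DMC only through its general safety review (continual under 7.9.1, with meetings every 3 months under 3.2).

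**Step 2. Narrow the uncovered group.** Deaths and second admissions are mandatory triggers. Life-threatening reactions, the top grade in SAP 10.6, are serious by definition (7.3.2 item 2), as is any inpatient admission (item 3). Item 6, the important medical event, could make many other severe reactions serious. What remains is severe reactions that the investigator judges non-serious and does not admit.

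**Step 3. Put sizes on it.** Section 7.9.1 gives no rate, so there is no plan figure to reproduce. Inputs: about 50 subjects randomized 1:1 (Protocol 3.1), so n = 25 on CPNA; moderate symptoms in about 15% and severe in under 1% of subjects (1.6.1). Subjects are taken as independent, and P(X ≥ 2) = 1 − (1 − p)^n − n·p·(1 − p)^(n−1).

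- Moderate, p = 0.15: expected 25 × 0.15 = 3.75; P(X ≥ 2) = 0.907. Excluding these is sensible.
- Severe, at the ceiling p = 0.01: expected 25 × 0.01 = 0.25; P(X ≥ 2) = 1 − 0.7778 − 0.1964 = 0.0258; P(X ≥ 3) = 0.0020.
- Two severe reactors in 25 is 8%, with exact 95% CI 1.0% to 26.0%. The lower limit is about the protocol's ceiling.

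The 0.0258 counts all severe reactors. If a share s of them is non-serious and not admitted, p becomes 0.01 × s. The documents give no s; over an assumed range:

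| s | P(at least 2 uncovered reactors) |
|---|---|
| 10% | 0.0003 |
| 25% | 0.0018 |
| 50% | 0.0069 |
| 100% | 0.0258 |

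So if the protocol's rate is right, the gap will rarely matter. It matters if that rate is too low, which is what a monitoring rule is there to detect.

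**Step 4. Does the admission rule stand in?** Assume a true severe rate of 10% with 25% of those subjects admitted. P(at least 2 severe reactors) = 0.73, while P(at least 2 admitted), with p = 0.10 × 0.25 = 0.025, is 0.13. With 10% or 50% admitted it is 0.03 or 0.36.

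**Step 5. Would a between-arm test serve?** Two-sided Fisher against 0 of 25 on placebo: 2 of 25 gives p = 0.490, 3 gives 0.235, 5 gives 0.0502, 6 gives 0.022. A test is too weak at this size; judgment by severity is needed.

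**The case against.** The strongest reply is that nothing is forbidden. The wording in 7.9.1 is permissive, the data shown to the DMC are not restricted, and 7.6.2 names the DMC among the bodies whose review may suspend treatment at a site, with no exclusion for dosing symptoms. The sponsor and FDA can suspend the whole study, and the sponsor can stop for any reason. Individual rules cover many severe reactors: Grade 3 or 4 reactions may end exposure (4.3.1), severe reactions in initial escalation end it (6.8.1), and two or more epinephrine doses halt up-dosing (6.8.3, 7.9.2). The 24-hour anaphylaxis reports were made at the DMC's request, so it already treats such reactions as its business. The Charter, still under development in 7.4, may settle the matter. All of this stands. It shows that power and visibility are intact; it does not supply a written study-level criterion for the remaining group.

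A reader might infer that serious dosing reactions are excluded too, or that the text leaves them open. The documents do not support that. An adverse event is "any untoward medical occurrence in humans, whether or not considered drug related which occurs during the conduct of a clinical trial" (7.3.1), 7.1 puts serious events on the AE/SAE form even when dosing caused them, and 3.7 lists SAEs apart from dosing symptoms. The natural reading is that SAEs count already.

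A reader might also want all dosing-related anaphylaxis that meets 7.7.2 written into the criterion. The documents give no rate for it. At assumed per-subject rates of 1%, 2%, 5% and 10%, the chance of two or more cases in 25 is 2.6%, 8.9%, 36% and 73%, so the noise could be slight or heavy. That is better left to the DMC.

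**Conclusion.** The point holds in a limited form. In the protocol and SAP, severe dosing reactions that are non-fatal, judged non-serious and not admitted meet no written study-level criterion, because the exclusion in 7.9.1 has no severity limit. The group is probably small, and its share of all severe reactions is unknown. The 2.6% chance of two or more severe reactors rests on 25 independent CPNA subjects and the 1% ceiling, and is an upper bound for the uncovered subset at that rate.

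It would be wrong to infer that the DMC is barred from acting or will not see these reactions; the wording of one criterion is at fault, not the oversight. The efficacy analysis is not affected. This is a cheap improvement of minor to moderate priority, conditional on what the Charter says.

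**What to change.** In 7.9.1, replace the closing exclusion with: *apart from non-serious dosing symptoms of mild or moderate severity*. Then add: *Severe (Grade 3 or higher, Table A4-3) or serious dosing reactions count toward the DMC's review of whether to recommend a halt, as a matter of judgment and not as an automatic trigger.* Refer to Table A4-3 and not to Appendix 3, whose staging would put stridor back under moderate. Put matching text in the DMC Charter, and leave any numeric trigger, and any rule for anaphylaxis, to the DMC and sponsor.

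The cost is two short edits, with no new committee, form or visit. Severity is already recorded at each escalation dose (SAP 10.6). For home dosing, SAP 10.7 describes only symptom descriptions and times, but 6.8.2 already has the site judge severity to choose the next dose. The downside is that the DMC must weigh an expected excess on CPNA by severity rather than set it aside.
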